9.3.3 Tertiary endpoints

9.3.3.1 Pulmonary function testing (PFT)

Pulmonary function testing will be performed at the time points specified in [Section 1.2](#). The PFT administration protocol is standardized across sites in accordance with the American Thoracic Society (ATS) guidelines (33). The PFT will include the assessment of FVC, forced expiratory volume in the first second of the FVC maneuver, maximal inspiratory pressure (MIP), maximal expiratory pressure (MEP), and peak expiratory flow in the upright and supine positions. Pulmonary function tests are not required for young patients unable to reliably undergo testing or for patients who are invasively ventilated, but missing assessments must be documented for analysis and potential impact on the study results.

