Two-dimensional and M-mode ECHO will be performed and a specified medium (eg, videotape or digital) will be sent to the core central cardiology laboratory for interpretation. A central cardiologist will review all ECHO. This person will be blinded to the patient and study time point. The primary cardiac outcome assessments (measured and derived by an external vendor Biomedical Systems) to be recorded using off-line review include: LVMI, LVM Z-score, left ventricle long axis, cross sectional area, end diastolic volume, end systolic volume, internal diameter, Septal wall diameter, Posterior wall diameter, Ejection Fraction, Left Ventricle sphericity, Left Ventricle thickness:dimension ratio, and Left Ventricle mass:volume ratio. M-mode parameters include: Left Ventricle Internal Dimension, Posterior Wall, Left Ventricle Internal Dimension, and Shortening Fraction. Systolic, Diastolic, and mean blood pressure will be determined. The following Tricuspid Valve/Mitral Valve parameters will also be assessed: Right Ventricular Pressure (by TR jet), TR gradient, Mitral Valve peak E, Mitral Valve peak A, E:A Ratio, and Mitral Valve deceleration time.

Eyelid position measurements

Study participants will have images taken of their eyes while wearing a pair of empty eyeglass frames with rulers attached as a standardized measurement tool at the time points specified in

Protocol Amendment 03 Version 1 Section 1.2. The following eyelid position measurements will be performed by the central reader:

- IPFD,
- MRD-1,
- MPD.

Creatine kinase

CK measurements will come from the central lab, including both total CK and CK with MB fraction.

Composite Score Constructed Considering 3 Domains: GMFM-88 and GMFCS-E&R, Ptosis, and Respiratory Function

The exploratory composite score will be constructed considering 3 domains: GMFM-88 and GMFCS-E&R, ptosis, and respiratory function (measured by the use of respiratory device). Within each domain, the change from baseline to Week 25 will be classified into improvement, unchanged, and worsening ([Appendix A](#)), and then receives a domain score which is determined by the baseline status and the change category according to [Table 1](#). The composite score is the sum of the 3 domain scores.

Table 1- Composite Score Constructed Considering 3 Domains: GMFM-88 and GMFCS-E&R, Ptosis, and Respiratory Function

Domain	Population	Change from Baseline		
		Improvement	Unchanged	Worsening

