Respiratory	Suboptimal clinical response/decline ^a	2	1	0
	No suboptimal clinical response/decline	1	0	-1
Motor skills	Suboptimal clinical response/decline ^b	2	1	0
	No suboptimal clinical response/decline	1	0	-1
Ptosis	Suboptimal clinical response ^c	2	1	0
	No suboptimal clinical response	1	0	-1

- a. Suboptimal clinical response is documented sustained decline in percent predicted FVC $\geq 15\%$ or new onset of non-invasive ventilator assistance (acquired for at least 4 weeks prior to study enrollment). If a patient is not old enough to perform PFT properly, assign a score of 0. Clinical decline is new development or worsening of respiratory failure requiring the use or increased use of ventilatory assistance (invasive or non-invasive). Ventilatory assistance must have been required for at least 4 weeks prior to study enrollment,
- b. Suboptimal clinical response is documented worsening of muscle strength demonstrated by a developmental plateau or decrease in GMFM-88 Total Score and/or in scaled scores of Pompe-PEDI scale or in other motor scale and/or clinical developmental evaluation tools. Use GMFM-88 only if the patient entered the cohort due to suboptimal clinical response on Pompe PEDI. Clinical decline for patients ≤ 2 years of age at study entry, is failure to acquire at least 2 new age appropriate gross motor milestones at least 6 months prior to study enrollment; for patients > 2 years of age at study entry, documented worsening of muscle weakness.
- c. Suboptimal clinical response is new onset of ptosis.

If a patient does not have any suboptimal response/decline at baseline for a domain (respiratory, motor skills, or ptosis), a score of 1, 0, or -1 is assigned if a patient improves, remains the same, or declines, respectively, with the exception of improvement for ptosis (which is not possible). Otherwise, if a patient has a suboptimal clinical response/decline at baseline for a domain (respiratory, motor skills, or ptosis), a score of 2, 1, or 0 is assigned if a patient improves, remains the same, or declines. It is under the rationale that stopping a declining trend shall be credited with a higher score.

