FVC will be reported in absolute value in liters. The FVC (% predicted) value is defined as $100^* (\text{actual FVC measurement}/\text{predicted value of FVC})$. The Quanjer GLI-2012 regression equations and lookup tables (1) are used to calculate predicted values of FVC. Predicted values of FVC are functions of sex, age in years (3-95 years), height in cm, and ethnic group (Whites, African Americans, South East Asians, North East Asians and for Other ethnic groups or people of mixed descent). FVC is predicted according to the following equation:

$$M = \exp(a_0 + a_1 \cdot \ln(\text{Height}) + a_2 \cdot \ln(\text{Age}) + a_3 \cdot \text{black} + a_4 \cdot \text{NEAsia} + a_5 \cdot \text{SEAsia} + a_6 \cdot \text{Other} + \text{Mspline})$$

Where

black = 1 if a subject is African American, otherwise = 0

NEAsia = 1 if a subject is from North East Asia, otherwise = 0

SEAsia = 1 if a subject is from South East Asia, otherwise = 0

Other = 1 if subject is 'other ethnic group' or mixed ethnicity, otherwise = 0

Coefficients a(n) depend on sex and are given by lookup table

Mspline is age-varying coefficients, given by lookup table for each type of sex

For the analysis purpose, the age will be calculated based on (assessment date - birth date + 1)/365.25. Height will be based on the most recent valid value at or prior to the assessment date.

The percent predicted values for MIP and MEP will be calculated (6, 7). The normal reference values used for percent predicted calculation will be dependent on each patient's age, gender, and weight (Table 3). For each patient, the same equations used for the baseline will be used to calculate the predicted values (eg, if a patient started at ≤ 17 years of age and turns 18 during the study, he/she will still use the pediatric formula after turning to 18). For analysis purposes, the age will be calculated based on (assessment date - birth date + 1)/365.25. Weight for age < 18 will be based on the most recent valid value at or prior to the assessment date. The percent predicted value is defined as $(\text{absolute measurement}/\text{normal reference value}) * 100$. Since the reference

values will be available only for patients of age 7 years or older, the percent predicted MIP and MEP will not be derived for patients aged <7.

Table 3 - Reference equations for predicted value of MEP and MIP

Test/Age at baseline	Male	Female
MEP		
≥18 years old (6)	174 – 0.83 * age	131 – 0.86 * age

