7–17 years old (7)	35 + 5.5 * age	24 + 4.8 * age
MIP		
≥18 years old (6)	120 – 0.41 * age	108 – 0.61 * age
7–17 years old (7)	44.5 + 0.75 * weight	40 + 0.57 * weight

Age in years; weight in kg.

All PFTs will be reported centrally from Biomedical Systems (BMS) following pulmonary software specification and user requirement (2).

Ventilator use diary

The Investigator will provide a respiratory diary to the patient (and/or the patient's parent[s]/legal guardian[s]) to record the daily use (if any) of mechanical ventilation (including both invasive and non-invasive) at daytime and nighttime. The date the patient first became dependent on invasive ventilator, as well as the reasons for first ventilator use will be collected and results will be recorded in the e-CRF. If the patient requires mechanical invasive or non-invasive ventilator support during the study, the start date, stop date, and reasons for each episode of continuous mechanical ventilator support will be collected. Invasive ventilation is defined as mechanical ventilatory support applied with the use of an endotracheal tube or tracheostomy, and noninvasive ventilation is defined as ventilatory support applied without the use of an endotracheal tube, i.e., no invasion of the airway. On a bi-weekly basis, the average number of hours of ventilator use/day will be calculated by the Investigator based on the ventilator use diary and data recorded until (1) ventilator support is no longer needed; (2) patient death; or (3) end of study (whichever occurs first). The date and reason that ventilator use is no longer needed will be recorded. The daily ventilator use diary is only required to be completed for patients using ventilator support.

If the patient requires any invasive or non-invasive mechanical ventilation (excluding planned ventilatory support less than 3 days duration for a planned surgical procedure), the Investigator will describe the events leading up to the mechanical ventilation using the ventilator use form/log in the e-CRF.

PedsQL Generic Core Scale questionnaire

The PedsQL Generic Core Scales is a general HRQOL tool. If patients are unable to complete this assessment, a parent proxy form will be used. During the treatment period, the assessment will be completed before IMP infusion if possible, and the patients will continue on the age-

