Handling of adverse events when date and time of first investigational medicinal product administration is missing

When the date and time of the first IMP administration is missing, all AEs that occurred on or after the day of randomization should be considered as TEAEs. The exposure duration should be kept as missing.

The last dose intake should be clearly identified in e-CRF and should not be approximated by the last returned package date.

Handling of missing assessment of relationship of adverse events to investigational medicinal product

If the assessment of the relationship to IMP is missing, then the relationship to IMP in the frequency tables is considered as possibly related, but no imputation should be done at the data level.

Handling of missing severity of adverse events

If the severity is missing for one of the treatment-emergent occurrences of an AE, the maximal severity on the remaining occurrences of the same patient will be considered. If the severity is missing for all the occurrences, a “missing” category will be added in the summary table.

Handling of potentially clinically significant abnormalities

If a patient has a missing baseline he will be grouped in the category “normal/missing at baseline”.

For PCSAs with 2 conditions, one based on a change from baseline value or a normal range and the other on a threshold value, with the first condition being missing, the PCSA will be based only on the second condition.

For a PCSA defined on a threshold and/or a normal range, this PCSA will be derived using this threshold if the normal range is missing; e.g., for eosinophils the PCSA is >0.5 GIGA/L or $>$ ULN if $ULN \geq 0.5$ GIGA/L. When ULN is missing, the value 0.5 should be used.

Measurements flagged as invalid by the laboratory will not be summarized or taken into account in the computation of PCSA values.

Handling of ADA titer with missing or non-numerical values

If the ADA titer is reported as “< value”, then the actual value is imputed as this value. For example, “<100” will be imputed as 100. A negative ADA status will be assumed as a value of 0 (will be excluded when geometric mean of the group needs to be calculated).

Handling of missing domains for the composite score

If any of the 3 domains including GMFM-88 and GMFCS-E&R, ptosis, and respiratory function, has missing data at baseline, the domain score of change from baseline at the end of PAP will be 0.

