7 LIST OF APPENDICES

[Appendix A](#): Classification of changes (including improvement, unchanged or worsening) from baseline to Week 25 for the 3 domains comprising the composite score

[Appendix B](#) Potentially clinically significant abnormalities (PCSA) criteria

Appendix A Classification of changes (including improvement, unchanged or worsening) from baseline to Week 25 for the 3 domains comprising the composite score (9).

Parameter	Baseline	Week 25		
		Improvement	Unchanged	Worsening
Respiratory	No use of any ventilation assistance	NA	No use of any ventilation assistance	Use of any ventilation assistance
	Use non-invasive ventilation assistance during daytime only or nighttime only	No use of any ventilation assistance	Use non-invasive ventilation assistance during daytime only or nighttime only	Use non-invasive ventilation assistance during both daytime and nighttime Use invasive ventilation assistance
	Use non-invasive ventilation assistance during both daytime and nighttime	No use of any ventilation assistance Use non-invasive ventilation assistance during daytime only or nighttime only	Use non-invasive ventilation assistance during both daytime and nighttime	Use invasive ventilation assistance
	Use invasive ventilation assistance during daytime only or nighttime only	No use of any ventilation assistance Use non-invasive ventilation assistance	Use invasive ventilation assistance during daytime only or nighttime only	Use invasive ventilation assistance during both daytime and nighttime
	Use invasive ventilation assistance during both daytime and nighttime	No use of any ventilation assistance Use non-invasive ventilation assistance Use invasive ventilation assistance <24 hrs/day	Use invasive ventilation assistance during both daytime and nighttime	NA
Motor Skills: GMFM-88 Total Score ^a	Level I Walker	Total Score increase ≥ 3.22	$-3.22 < \text{Total Score change} < 3.22$	Total Score decrease ≥ 3.22
	Level II Supported walker	Total Score increase ≥ 2.76	$-2.76 < \text{Total Score change} < 2.76$	Total Score decrease ≥ 2.76
	Level III Supported stander	Total Score increase ≥ 1.41	$-1.41 < \text{Total Score change} < 1.41$	Total Score decrease ≥ 1.41
	Level IV Sitter	Total Score increase ≥ 1.65	$-1.65 < \text{Total Score change} < 1.65$	Total Score decrease ≥ 1.65
	Level V Restricted antigravity movement	Total Score increase ≥ 0.8	$-0.8 < \text{Total Score change} < 0.8$	Total Score decrease ≥ 0.8

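### Composite score: a domain missing at baseline scores 0, which means worsening if that domain was suboptimal, and Table 1 footnote a can overwrite ventilator data that were observed

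*SAP*

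**What the plan says.** SAP 2.1.6 builds the composite as the sum of three domain scores: respiratory, motor and ptosis. Table 1 has two rows per domain. If the domain was suboptimal or declining before the study, "a score of 2, 1, or 0 is assigned if a patient improves, remains the same, or declines"; otherwise the scores are 1, 0 and -1. The SAP explains the extra point as credit for halting a decline.

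Two default rules produce a 0 outside that grid.

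- SAP 2.5.2, on missing domains: if any of the three "has missing data at baseline, the domain score of change from baseline at the end of PAP will be 0". The rule does not mention the Table 1 row.
- SAP 2.1.6, Table 1 footnote a, inside the definition of a respiratory suboptimal response: "If a patient is not old enough to perform PFT properly, assign a score of 0".

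Respiratory change itself does not use pulmonary function. SAP 2.1.6 names the domain as "respiratory function (measured by the use of respiratory device". Appendix A classifies it by ventilation categories only, for example "Use non-invasive ventilation assistance during daytime only or nighttime only". SAP 2.1.9 has families keep a diary "to record the daily use (if any) of mechanical ventilation (including both invasive and non-invasive) at daytime and nighttime".

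**The concern.** The same 0 carries two meanings. In the row for domains that were not suboptimal it says nothing changed. In the suboptimal row it is the lowest score available and says the child worsened. A child whose domain was documented as suboptimal, but who lacks a study baseline value for it, is therefore given the worst result in the row, even if the domain held steady or improved. That runs against the SAP's own reason for having two rows.

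Footnote a raises a different problem. If its 0 is the respiratory domain score, it replaces a change that can be classified from ventilator status at any age. Two programmers could derive different composites from the same record.

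The composite difference carries the only hypothesis test planned between the randomised arms (SAP 3). With about five patients per arm, a mis-scored patient is visible in the arm mean.

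**Working it through.** **Inputs.** Table 1 scores: 2, 1, 0 (suboptimal or declining row) and 1, 0, -1 (other row). Default score: 0. Arm size: 5, from at least 10 patients randomised 1:1 (SAP 1.1). The plan states no figure for this point, so there is none to reproduce.

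**Step 1: what 0 means in each row.** In the suboptimal row only *worsening* equals 0; it lies 1 below *unchanged* and 2 below *improvement*. In the other row only *unchanged* equals 0.

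**Step 2: effect of one defaulted domain on a 5-patient arm mean.** Shift = (0 - Table 1 score) / 5.

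| True change | Suboptimal row | Other row |
|---|---|---|
| Improvement | (0 - 2)/5 = -0.4 | (0 - 1)/5 = -0.2 |
| Unchanged | (0 - 1)/5 = -0.2 | (0 - 0)/5 = 0 |
| Worsening | (0 - 0)/5 = 0 | (0 - (-1))/5 = +0.2 |

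Some cells cannot occur. Appendix A allows no improvement from no ptosis or from no ventilation.

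**Step 3: can a suboptimal domain lack a baseline value?** Yes. The row comes from chart review of assessments made before entry (Protocol 10.1.1; inclusion criteria I 06 and I 07), whereas change needs a study baseline value. The mITT definition (SAP 2.3.2) asks for an evaluable baseline efficacy assessment without saying all three domains, so such a patient stays in the analysis. Ptosis is one possible route: eyelid photographs need a separate consent (Protocol 9.2.2.5). That route applies only if the ptosis categories are read from the photographs, which the SAP does not say.

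**Step 4: footnote a.** It can apply. Inclusion sets no lower age limit, Protocol 9.3.3.1 says "Pulmonary function tests are not required for young patients unable to reliably undergo testing", and the predicted FVC equations start at 3 years (SAP 2.1.9). The wording admits three readings. Scores for a child too young for testing:

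| Respiratory course to Week 25 | 0 is the domain score | Child forced into the other row | 0 means only no FVC-based response |
|---|---|---|---|
| New non-invasive ventilation before entry, then none | 0 | 1 | 2 |
| New non-invasive ventilation, unchanged | 0 | 0 | 1 |
| New non-invasive ventilation, then invasive | 0 | -1 | 0 |
| No ventilation throughout | 0 | 0 | 0 |
| No ventilation, then some | 0 | -1 | -1 |

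Only the last column follows Table 1 and Appendix A throughout. The first column scores a child who comes off ventilation the same as one who moves to invasive support.

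**Step 5: effect on the planned test.** Both triggers, a missing baseline value and being too young for testing, are facts about the child before treatment. Protocol 8.4 has randomisation follow the screening and baseline assessments, and the rules are the same in both arms. With no treatment effect, each child's score is then the same whichever arm is assigned, so the re-randomisation test in SAP 2.4.8 keeps its validity. The loss is one of information: a domain fixed at 0 cannot reflect anything that happened during treatment.

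**The case against.** **The missing-baseline case should be rare.** Entry on ptosis already needs at least two sequential assessments. Baseline is the last non-missing value before the first infusion, and eyelid measurement is scheduled at both screening and Day 1. Appendix A grades ptosis as none, one eye or both, with no millimetre cut-off, so it may be taken from clinical or chart findings and not from photographs. This stands. The documents give no event rate, and the size above is per case.

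**Footnote a is a drafting matter.** It hangs on the row label and sits within a definition of baseline status, so the harmless reading is available. This also stands, but the words used are an instruction to assign a score, and one sentence would settle it.

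**Scoring a missing baseline as unchanged is an imputation**, whereas SAP 2.5.2 says missing baselines are in general not imputed. True, but the present 0 also stands in for an unobserved change, and in the suboptimal row it picks the worst category. Reporting bounds meets the objection.

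**A reader might infer that the defaults tilt the comparison towards one drug.** The documents do not support that. As Step 5 shows, the triggers are baseline facts handled alike in both arms.

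**Conclusion.** Two scoring rules need correction or clarification. The rule in SAP 2.5.2 mis-scores a suboptimal domain with no baseline value. Each case moves a 5-patient arm mean by 0 to -0.4 relative to the Table 1 score. Footnote a, if read as the domain score, discards observed ventilator change, giving for example 0 instead of 2 or 0 instead of -1. These sizes are exact given Table 1 and five patients per arm; how often they arise is unknown and, for the first rule, probably low. Severity is minor: the composite is exploratory, its p-values are references only (SAP 2.4.8) and the study is not confirmatory (SAP 2.4.8.1).

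A stronger reading is tempting. Every suboptimal cell is exactly 1 above its counterpart, so, default scores apart, the composite equals the sum of the changes plus the number of domains suboptimal at entry. A reader might infer that the planned test is biased by that number. It is not. The extra point is a declared choice (SAP 2.1.6; Protocol 11.4.3 says the score depends on baseline status), and in Cohort 3 the number is a baseline quantity covered by randomisation. Whether it adds or removes noise turns on change rates that the documents do not give. Over assumed inputs running from nearly stable to strongly worsening suboptimal domains, the variance of the composite relative to the change-only sum ran from 2.51 down to 0.62. Pooling with Cohorts 1 or 2 is only optional. The underlying chart-review items are already summarised by cohort and arm (SAP 2.1.1 and 2.4.1). What is not listed is the per-domain suboptimal flag. SAP 2.4.1, read literally, also leaves out a control patient who never receives avalglucosidase alfa.

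**What to change.** 1. **SAP 2.5.2.** Score a domain missing at baseline as unchanged within the patient's own Table 1 row: 1 if suboptimal or declining, 0 if not. Add a sensitivity analysis at the worst and best category that Appendix A permits, and report the number of defaulted domains by arm.
2. **Table 1 footnote a.** Classify respiratory change from ventilator status at all ages. Either state that the 0 means only that no FVC-based suboptimal response can be documented, or delete it.
3. **Optional, not an error.** Tabulate the per-domain suboptimal flags by arm and cohort for all mITT and safety patients, including controls who never receive avalglucosidase alfa. Label any pooling with Cohorts 1 or 2 as non-randomised.

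Cost: two changes of wording, two sensitivity runs and a count by arm, plus one table if item 3 is adopted. No new data are needed and Table 1 stays as it is. The downside is that unchanged is itself an imputed category, which is why both bounds should be shown.
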